8.1.4.6 Analysis on observed cases

An observed case (OC) analysis will additionally be conducted, where only observed data for study participants who are still on the randomized treatment at Week 16 are included. Study participants with missing data and all data after date of treatment discontinuation will be treated as missing and missing data will not be imputed. The same model than the one used for the primary efficacy analysis will be conducted on the RS. The following 4 attributes describe the estimand that will be used to define the treatment effect of interest for this analysis:

- Population = Study participants enrolled according to the protocol-specified inclusion/exclusion criteria and randomized to IMP
- Study participant-level outcome = ASAS40 at Week 16
- Intercurrent event handling = A "while on randomized treatment" strategy will be implemented.
- Population-level summary measure = Conditional odds ratio comparing bimekizumab to placebo.

Refer to Section 4.2.1.10 for further details.

8.1.4.7 Tipping point analysis

The degree of the departure from the missing at random (MAR) assumption to overturn conclusions from the primary analysis will be investigated in a tipping point sensitivity analysis. This analysis will be performed only if the primary analysis is significant at $\alpha=0.05$. In this analysis, it will be assumed that study participants who have missing data and are randomized to bimekizumab have a lower probability of response compared to study participants who have missing data and are randomized to placebo.

This analysis will generally follow the steps for multiple imputation described in Section 4.2.1.4.1. However, data for study participants after date of discontinuation of treatment will be changed to missing prior to imputation, but will not be changed to non-response after imputation, and all imputed values will be "adjusted" prior to calculating the binary response.

For the worst-case scenario, study participants who have missing ASAS40 response (after setting data after date of discontinuation of study treatment for any reason as defined in Section 3.4 to missing) and are randomized to bimekizumab are set to non-responders and study participants with missing data and randomized to placebo are set to responders. If the result tips from statistically significant to statistically insignificant, then the delta adjustment tipping point analysis will be conducted where missing and imputed values for each component of the ASAS40 endpoint are delta-adjusted. For both analyses, the same model as used for the primary efficacy analysis will be conducted on the RS. More robust primary analysis results will require larger adjustments to tip the results from significant to not significant.

Refer to Section 4.2.1.8 for more details on the methodology.

8.1.4.8 Analyses including COVID-19 impact

To assess the impact of the COVID-19 pandemic on the primary efficacy endpoint, the following sensitivity analyses will be conducted using the same analysis method as the primary analysis described in Section 8.1.2:

- On the COVID-19 free set,
- By timing of the Week 16 Visit relative to the start and end of the COVID-19 pandemic (ie, study participants will be categorized according to if their Week 16 Visit took place prior to, during or after the pandemic). See Section 3.2.2.2 for definition of pandemic periods.

For this last analysis, the same model than the one described in Section 8.1.3 will be used. The ORs and associated 95% CI results of this analysis will be displayed on a forest plot.

8.2 Statistical analysis of the secondary efficacy variables

8.2.1 Derivation of secondary efficacy variables

8.2.1.1 Other assessment in Axial SpondyloArthritis international Society response criteria (ASAS20, ASAS5/6, and ASAS-PR)

The ASAS20 response is defined as relative improvement of 20%, and an absolute improvement of at least 1 unit on a 0 to 10 NRS in at least 3 of the 4 following domains:

- Patient's Global Assessment of Disease Activity (PGADA)
- Pain assessment (total spinal pain, question 1 from total and nocturnal spinal pain)
- Function (represented by the Bath Ankylosing Spondylitis Functional Index (BASFI))
- Inflammation (represented by the mean of the Bath Ankylosing Spondylitis Disease Activity Index (BASDAI) questions 5 and 6) concerning morning stiffness intensity and duration)

and absence of deterioration in the potential remaining domain. A deterioration will be defined as a relative worsening of at least 20% and an absolute worsening of at least 1 unit.

The ASAS 5/6 response is defined as at least 20% improvement in 5 of 6 domains, which includes, in addition to the 4 domains mentioned above for ASAS20, spinal mobility (ie, lateral spinal flexion component of the BASMI) and hs-CRP as more objective measures.

The ASAS-PR response is defined as a score of ≤ 2 units on a 0 to 10 unit scale in all 4 domains listed above for ASAS20.

ASAS40 response in the TNF alpha inhibitor-naïve study participants represents the ASAS40 response for study participants with "Prior TNF α inhibitor = No" (which are defined per actual information on prior use of TNF α inhibitor). For the supportive analysis based on MI, all randomized study participants will be included in the imputation model (since this analysis is a subgroup analysis of the primary endpoint), but the analysis step will only be done on the subgroup of TNF alpha inhibitor-naïve study participants.

8.2.1.2 Bath Ankylosing Spondylitis Disease Activity Index (BASDAI)

As mentioned in Section 8.1.1.4, the BASDAI consists of six 10-unit NRSs measuring the disease activity of AS over the past week on 5 major symptoms. To give each symptom equal weighting, the average of the 2 scores relating to morning stiffness is taken. The BASDAI is calculated as follows:

$$BASDAI = \frac{Q1 + Q2 + Q3 + Q4 + \left(\frac{Q5 + Q6}{2} \right)}{5}$$

where Q1 – Q6 are the six questions from the BASDAI questionnaire.

The BASDAI score is between 0 and 10, with lower scores indicating lower disease activity.

As mentioned in Section 8.1.1.4, if 1 of the 2 morning stiffness measurements (ie, questions Q5 and Q6) is missing, the other one will be used for the morning stiffness calculation.

If one major symptom of the BASDAI is missing, the total score of the remaining symptoms will be divided by the number of symptoms assessed. If more than one major symptom is missing, the total BASDAI score will be set to missing.

8.2.1.3 Ankylosing Spondylitis Disease Activity Score major improvement (ASDAS-MI)

The ASDAS-CRP consists of a number of assessments which are scored by the study participant and physician and multiplied by a proven formula (van der Heijde et al, 2009) as shown below:

- 0.121 x Back pain (BASDAI Question 2 result)
- 0.058 x Duration of morning stiffness (BASDAI Question 6 result)
- 0.110 x Patient's Global Assessment of Disease Activity (PGADA)
- 0.073 x Peripheral pain/swelling (BASDAI Question 3 result)
- 0.579 x (natural logarithm of the (hs-CRP [mg/L] +1))

Back pain, PGADA, duration of morning stiffness, peripheral pain/swelling and fatigue are all assessed on a numerical scale (0 to 10 units) (Lukas et al, 2009). If the hs-CRP value is <2 mg/L, the constant value of 2 mg/L should be used in the calculation. The sum of these weighted components gives the ASDAS-CRP.

For analyses with imputation of missing data, the imputed value for ASDAS-CRP will be based on the imputed values for the individual components.

For observed case analyses, if any individual component score is missing, then the ASDAS-CRP will be set to missing.

Disease activity categories based on ASDAS-CRP are as follows:

- ASDAS-Inactive Disease (ASDAS-ID): ASDAS-CRP <1.3
- ASDAS-Low Disease (ASDAS-LD): ASDAS-CRP ≥1.3 to <2.1
- ASDAS-High Disease Activity (ASDAS-HD): ASDAS-CRP ≥2.1 to ≤3.5
- ASDAS-very High Disease Activity (ASDAS-vHD): ASDAS-CRP >3.5

The variables related to ASDAS improvement are defined as follows:

- ASDAS-Clinically Important Improvement (ASDAS-CII): ASDAS-CRP reduction (improvement) of ≥1.1 relative to Baseline
- ASDAS-Major Improvement (ASDAS-MI): ASDAS-CRP reduction (improvement) of ≥2.0 relative to Baseline

For both ASDAS disease category and ASDAS improvement variables, multiple imputation methods will be used to impute the ASDAS-CRP value and then dividing into the appropriate category or improvement groups.

8.2.1.4 Nocturnal spinal pain (NSP)

The pain in the spine at night due to AS will be measured by the study participant in answering question 2 of the total and nocturnal spine questionnaire “How much pain of your spine due to spondylitis do you have at night?”. To answer the question, the study participant will consider the average amount of pain in the preceding week and use a NRS ranging from 0 to 10, where 0 represents “no pain” and 10 represents “most severe pain”.

8.2.1.5 Ankylosing Spondylitis Quality of Life (ASQoL)

The ASQoL consists of 18 items which are scored by the study participant, each item with a score of 0=no or 1=yes. A score of "1" is given where the item is affirmed, indicating adverse quality of life. The ASQoL total score is based on the sum scores, ranging from 0 to 18, with higher scores indicating worse quality of life.

If 3 or fewer items are missing, the missing responses will be imputed with the mean of the available responses from that visit to calculate a total score. If more than 3 items are missing, the total score will be left missing.

8.2.1.6 Short-Form 36-item Health Survey (SF-36) Physical Component Summary (PCS)

The SF-36 (version 2, standard recall) is a 36-item generic health-related quality of life (HRQoL) instrument that uses a recall period of past 4 weeks. Items are grouped into the following 8 health domains: Physical Functioning (10 items), Role Physical (4 items), Bodily Pain (2 items), General Health (5 items), Vitality (4 items), Social Functioning (2 items), Role Emotional (3 items), Mental Health (5 items). The concepts represented by these domains contribute to physical, mental and social aspects of HRQoL. [REDACTED]

In addition to domain scores, the PCS and MCS scores are calculated from the 8 domains (excluding the Health Transition item). Component scores appreciate the impact of each domain on physical and mental health status (Maruish, 2011).

The two SF-36 component summaries (PCS and MCS) and the 8 domain scores are standardized with a mean of 50 and a standard deviation (SD) of 10 in the general US population (Maruish, 2011). An individual respondent's score that falls outside the T-score range of 45 to 55 should be considered outside the average range for the U.S. general population. When considering group-level data, a score below 47 should be considered indicative of impaired functioning within that health domain or dimension. Similar to individual respondent data, group mean scores 47 or greater should be considered average or above average as compared to the general US population.

For the calculation of the SF-36 domain scores and the two component summary scores, the scoring software QualityMetric's Health Outcomes™ will be used. The software uses updated 2009 U.S. population norms and applies a Full Missing Score Estimation method as follows:

- A health domain score (except the Physical Functioning domain) will be estimated provided that at least one non-missing response is available within that domain

- For the Physical Functioning domain item response, theory will be used to develop a model for estimates of the missing score
- Regression methods are then applied to estimate the PCS and MCS on the basis of the domain scores

8.2.1.7 Bath Ankylosing Spondylitis Disease Metrology Index (BASMI)

The BASMI characterizes the spinal mobility of study participants with AS consisting of 5 clinical measures to reflect study participant axial status: cervical rotation; tragus to wall distance; lateral spinal flexion; modified Schober test; intermalleolar distance. Each of the 5 movements is scored according to the linear BASMI definition given in [Table 8-1](#). The mean of the 5 scores provides the BASMI score. The BASMI score ranges from 0 to 10. The higher the BASMI score the more severe the study participant's limitation of movement due to their AS.

Table 8-1: BASMI linear definition

Clinical Movement	S = 0 if:	S between 0 and 10:	S=10 if:
Lateral spinal flexion* (cm)	$A \geq 21.1$	$S = (21.1 \text{ cm} - A) / 2.1 \text{ cm}$	$A \leq 0.1$
Tragus-to-wall distance* (cm)	$A \leq 8$	$S = (A - 8 \text{ cm}) / 3 \text{ cm}$	$A \geq 38$
Lumbar Flexion* (modified Schober) (cm)	$A \geq 7.4$	$S = (7.4 \text{ cm} - A) / 0.7 \text{ cm}$	$A \leq 0.4$
Intermalleolar distance (cm)	$A \geq 124.5$	$S = (124.5 \text{ cm} - A) / 10 \text{ cm}$	$A \leq 24.5$
Cervical rotation angle* (°)	$A \geq 89.3$	$S = (89.3^\circ - A) / 8.5^\circ$	$A \leq 4.3$

S = BASMI Score, A = assessment.

* For cervical rotation, tragus-to-wall distance, and lateral spinal flexion, the mean of the left and right measurements will be calculated, if both are available. Otherwise, the available measurement will be used. If multiple attempted measurements are obtained, calculate the mean of the attempts. The mean of the attempts should be calculated after averaging the left and right measurements, where applicable.

From van der Heijde et al. 2008.

For all clinical measures, values outside the ranges presented in [Table 8-2](#) (Maksymowych 2006) will be flagged as invalid and treated as if they were missing values. Where two attempted measurements for a single clinical measure are entered at a given visit (ie, lateral lumbar flexion, cervical rotation, tragus-to-wall distance, and lumbar flexion) and only one attempted measurement is valid, the valid measurement will be used. If both attempts are invalid, the measure will be treated as missing.

Table 8-2: BASMI linear definition (pre-defined ranges)

Clinical Movement	Range*
Lateral spinal flexion (mean right/left)	0.75 – 25.00 cm
Tragus-to-wall distance (mean right/left)	9.00 – 37.50 cm
Lumbar flexion (modified Schober)	0.00 – 9.00 cm

Clinical Movement	Range*
Intermalleolar distance	13.00 – 160.00 cm
Cervical rotation (mean right/left)	0.00 – 94.00°

* From Maksymowych 2006

The order of events to derive the BASMI scores is as follows:

1. Discard individual assessment values (A) that are invalid (out of range according to the [Table 8–2](#) above)
2. Average remaining valid left and right assessment values (A) by study participant, analysis visit, parameter and attempt, if more than one valid value is present
3. Average assessment values (A) across attempts, by study participant, analysis visit and parameter, if more than one attempt is present with valid values
4. From these averaged (A) values, calculate a single BASMI component score (S), by study participant, analysis visit and parameter
5. Re-map early termination visits according to the specifications given in [Section 3.2.3](#), Re-mapping will be performed on a per-parameter basis prior to the calculation of the BASMI score (this method is adopted in the event that not all parameters are assessed at each visit)
6. If 1 or 2 BASMI components scores (S) are missing for a given study participant and analysis visit, carry forward the most recent non-missing value for that study participant and component to the current analysis visit; it is allowed to carry forward a screening or Baseline score value (S) to a post-Baseline analysis visit
7. If one value is available for each of the 5 component scores for a given study participant and analysis visit, calculate BASMI score as the average of the 5 component scores (S); otherwise set the BASMI score to missing for that study participant and analysis visit

8.2.2 Analysis of secondary efficacy variables

The secondary efficacy variables will be analyzed for all study participants in the RS as summarized in [Table 4-1](#).

As indicated in [Section 4.5](#), there are 11 key secondary endpoints included in the testing hierarchy that will be tested successively one after the other if the previous endpoint was found to be statistically significant.

Three secondary endpoints (change from Baseline in BASMI at Week 16, change from Baseline in MASES index at Week 16 in the subgroup of study participants with enthesitis at Baseline, and enthesitis-free state at Week 16 based on the MASES Index in the subgroup of study participants with enthesitis at Baseline) will not be part of the testing hierarchy and for this reason the p-values produced by the statistical models will be considered nominal since these endpoints are not controlled for multiplicity. The following analyses will be conducted for the Secondary Efficacy Endpoints:

- For the secondary binary endpoints:
 - Composite Estimand - NRI: The same composite estimand structure as the one defined in [Section 8.1.2](#) for the primary efficacy analysis will be used. The same analysis model will be considered, and the analysis results will be presented similarly as for the primary efficacy analysis. The imputation strategy for handling missing data will be the same as for the primary endpoint, ie the NRI approach (see [Section 4.2.1.1](#)).
 - Modified Composite - MI: A similar modified composite estimand structure as the one defined in [Section 8.1.4.4](#) for the primary efficacy analysis will be used. The same analysis model will be considered, and the analysis results will be presented similarly as for the primary efficacy analysis. The imputation strategy for handling missing data will be the MI-MCMC/Monotone regression for the composite and non-composite binary endpoints as detailed in [Section 4.2.1.4](#).
 - Observed Case: A similar analysis as the one defined in [Section 4.2.1.10](#) for the primary efficacy analysis will be used.
- For the secondary continuous endpoints:
 - Reference-Based Estimand - MI: The same hypothetical estimand ([Section 4.2.1.6](#)) structure as the one defined in [Section 8.1.4.3](#) for the analysis on component variables for the primary efficacy endpoint will be used. The same analysis model and imputation strategy for handling missing data will also be considered. The analysis results will be presented similarly as for this analysis on the individual ASAS40 components.
This estimand will only be implemented for the secondary continuous endpoints in the testing hierarchy.
 - Hypothetical Estimand - MI:
The following 4 attributes describe the estimand that will be used to define the treatment effect of interest for this analysis:
 - Population = Study participants enrolled according to the protocol-specified inclusion/exclusion criteria and randomized to IMP

- Study participant level outcome = The change from Baseline in the variable at Week 16
- Intercurrent event handling = An intercurrent event is defined as discontinuation of study treatment due to any reason prior to Week 16. A hypothetical strategy will be implemented in which the estimand targets the treatment difference in a scenario where intercurrent does not occur, such that outcomes for study participants without an intercurrent event are as observed, and outcomes for study participants with an intercurrent event are treated as though they had completed the randomized study treatment through Week 16. A multiple imputation (MI) strategy will be used to impute any missing data including observed data after the IE date which will be set to missing prior to running MI.
- Population-level summary measure = the difference in the adjusted means between bimekizumab and placebo.

The same analysis model as the one defined in Section 8.1.4.3 used for the analysis on the individual ASAS40 components will be considered. The analysis results will also be presented similarly.

- Observed Case: A similar analysis as the one defined in Section 4.2.1.10 for the primary efficacy analysis will be used.

Note that the ANCOVA analysis on the change from Baseline in BASFI will be considered a supportive analysis for the primary endpoint since BASFI is one of the components of the primary endpoint.

An overview table will combine the results of the primary analysis for the primary efficacy endpoint and the results of the primary analysis for each key secondary endpoint.

Subgroup analyses will also be conducted for ASDAS-MI endpoint using NRI. The variables of interest will be age, gender, race, region, ASDAS status and prior TNF α inhibitor exposure. Exact definition of the subgroups is provided in Table 4-4. The same methodology as the one used for the ASAS40 subgroup analyses will be followed. The results obtained for each subgroup will be combined in one single table as well as presented on a forest plot.

Finally, to assess the impact of the COVID-19 pandemic, the primary analysis of all secondary efficacy endpoints included in the testing hierarchy will be analyzed on the COVID-19 free set, using the Reference-Based Estimand.

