4 STATISTICAL/ANALYTICAL ISSUES

4.1 Adjustments for covariates

The primary efficacy analysis that will investigate the treatment effect will be adjusted for:

- Prior TNF α inhibitor exposure (yes, no), and
- Region (Asia, Eastern Europe, North America, Western Europe)

However, prior TNF α inhibitor exposure may be dropped from the model in order to achieve model convergence (ie, in case the likelihood maximization algorithm failed to converge). If convergence is still not obtained, then region may instead or also be dropped from the model. This will be decided at the time of the table creation and clarified in respective table footnotes. Finally, in the case of the continuous secondary endpoints of the testing hierarchy, if the

reference-based multiple imputation model still does not converge, the analysis will be replaced using LOCF as imputation method (see Section 4.2.1.11)

Prior TNF α inhibitor exposure and region are the stratification factors of the randomization. In the event that a study participant is stratified in the incorrect stratum (ie, the stratum recorded in the Interactive voice or web Response System (IXRS) differs from the actual stratum the study participant belongs to), the actual stratum will be used for the analysis.

The secondary analyses will be adjusted on the same categorical factors as the primary analysis. For continuous variables, Baseline value (of the variable of interest) will also be included as covariate where appropriate.

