One indicator variable (region1) will be defined as 0 for regions other than North America and 1 for North America. Two more indicator variables (region2 and region3) will be defined similarly replacing North America with Eastern Europe and Western Europe respectively. In the VAR statement of the imputation model, the indicator variables will be ordered as follows: region1 region2 and region3. In the eventuality that two regions required to be pooled due to a low percentage of study participants randomized in one region (see Section 3.8), the indicator variables defined above will be revised accordingly.

- One indicator variable will be defined for the prior TNF α inhibitor exposure stratification variable: will be coded as 1 for yes and 0 for No.

To maintain consistency with the MCMC method for intermittent missing values, these indicator variables will also be used in the monotone regression step for monotone missing values and treated as continuous variables.

- Step 3: For each of the 100 complete imputed data set obtained from Step 2, the binary responder variable will be derived. In practice, the value at the week of interest (eg, Week 16) in the imputed data sets will be used to categorize the study participant as a responder or not. If study participants have a treatment discontinuation due to AE or lack of efficacy, then the endpoint will be changed to “non-response” for all visits after the IE date.
- Step 4:
 - For secondary efficacy endpoints: For each of the datasets obtained in Step 3, the responder rate will be analyzed using a logistic regression model with factors of treatment group, region, and prior TNF α inhibitor exposure as fixed effects. The suitability of including region and prior TNF α inhibitor exposure at Baseline as fixed effects will be assessed using goodness-of-fit tests (Deviance and Pearson’s and Hosmer-Lemeshow) and added if appropriate and allows model convergence.
 - For other efficacy binary endpoints: At each timepoint, the mean proportion of the responders and 95% CIs will be calculated from the imputed datasets using SAS® PROC MIANALYZE.

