A logistic regression model will be used to assess the treatment effect on ASAS40 response at Week 16. The model will include fixed effects for treatment, and prior TNF α inhibitor exposure and region as stratification factors. The suitability of including these variables in the model will be assessed using the Hosmer-Lemeshow goodness-of-fit test.

Also, as mentioned in Section 4.1, if the logistic regression model is unable to converge the stratification factors may be dropped to facilitate the model convergence.

The SAS[®] PROC LOGISTIC will be used to run the logistic regression.

The summary table results will present the number of responders, adjusted responder rates and associated 95% CI for bimekizumab and placebo, the adjusted odds ratio and 95% CI for the comparison bimekizumab versus placebo, and the p-value that the OR=1. The treatment comparison will be made using the 2-sided Wald test at a significance level of $\alpha=0.05$.

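### ASDAS-MI depends on Baseline ASDAS-CRP by construction, but its logistic model omits that Baseline: a small, avoidable loss of efficiency in a valid analysis

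*SAP*

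**What the plan says.** SAP section 8.2.1.3 defines the endpoint: "ASDAS-Major Improvement (ASDAS-MI): ASDAS-CRP reduction (improvement) of ≥2.0 relative to Baseline". The same section puts a floor under the CRP term: "If the hs-CRP value is <2 mg/L, the constant value of 2 mg/L should be used in the calculation".

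For secondary binary endpoints, section 8.2.2 refers back to the primary analysis: "The same analysis model will be considered, and the analysis results will be presented similarly as for the primary efficacy analysis". Section 8.1.2 gives the terms of that model: "The model will include fixed effects for treatment, and prior TNF α inhibitor exposure and region as stratification factors". The supportive multiple-imputation analysis has the same terms; section 4.2.1.4.1 specifies a "logistic regression model with factors of treatment group, region, and prior TNF α inhibitor exposure as fixed effects".

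Section 4.1 states the general covariate policy. On factors: "The secondary analyses will be adjusted on the same categorical factors as the primary analysis". On Baseline: "For continuous variables, Baseline value (of the variable of interest) will also be included as covariate where appropriate". ASDAS-MI is analysed as a binary variable, so the second rule does not reach it.

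Baseline ASDAS appears elsewhere in three places. It is tabulated by arm (section 6.2.1). It defines a subgroup for ASDAS-MI by ASDAS status (section 8.2.2, with the method in 8.1.3). Change in ASDAS-CRP at Week 16 also gets a nominal test (section 8.3.3), under an ANCOVA with Baseline as covariate. None of these is the hierarchical test of ASDAS-MI.

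**The concern.** ASDAS-MI is a change score cut at a fixed absolute value, taken from a scale with a lower bound. Someone who starts low has little or no room to fall by 2.0, whatever the treatment, so Baseline is tied to response by definition. The SAP adjusts continuous change scores for their Baseline; cutting a change score at 2.0 does not remove its dependence on Baseline.

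Two things are at stake. First, the Wald test for ASDAS-MI has less power than it could have. The endpoint sits in the fixed sequence of section 4.5, where a failure stops all later tests, and section 2.4.2 lists further endpoints after it. Second, if the arms differ by chance in Baseline ASDAS-CRP, the reported treatment comparison carries that difference. This matters even when the test succeeds.

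**Working it through.** **1. The plan's own power figure.** Inputs from section 2.4: 200 vs 100 participants, 36.0% vs 13.8%, two-sided 0.05, continuity-corrected chi-square, stated power 98%.

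- Pooled rate: (200 × 0.36 + 100 × 0.138) / 300 = 0.286.
- SE under the null: √[0.286 × 0.714 × (1/100 + 1/200)] = 0.0553.
- SE under the alternative: √[0.138 × 0.862/100 + 0.36 × 0.64/200] = 0.0484.
- Continuity correction: (1/100 + 1/200)/2 = 0.0075.
- Power: Φ[(0.222 − 0.0075 − 1.96 × 0.0553)/0.0484] = Φ(2.19) = 98.6%. Without the correction it is 99.1%.

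The stated figure reproduces.

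**2. The built-in link to Baseline.** Put zero in every patient-reported term of the section 8.2.1.3 formula and the floor of 2 mg/L in the CRP term: 0.579 × ln(2 + 1) = 0.636. A fall of 2.0 therefore needs a Baseline of at least 2.636. Two of the four ASDAS status categories in Table 4-4 (below 1.3, and 1.3 to 2.1) cannot contain a responder, nor can the lower part of the third. The SAP does not say how many participants lie there. If Baseline were about N(3.7, 0.8), an assumption, the share would be Φ[(2.636 − 3.7)/0.8] = Φ(−1.33), or about 9%.

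**3. What adding Baseline changes.** The SAP gives no correlation between Baseline and improvement, so r = 0.2 to 0.5 is assumed (an odds ratio of about 1.4 to 2.7 per Baseline SD). Improvement and Baseline were simulated as bivariate normal with the marginal response rates held fixed. Each setting had 4,000 trials of 200 vs 100, with a logistic Wald test and no stratification factors in either model.

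| r | Power at 36% vs 13.8%, without → with | Variance ratio of rate difference | Power at 28% vs 13.8%, without → with |
|---|---|---|---|
| 0.2 | 99.0 → 99.2% | 0.983 | 81.9 → 82.4% |
| 0.3 | 98.9 → 99.2% | 0.963 | 80.7 → 81.7% |
| 0.4 | 98.9 → 99.3% | 0.934 | 81.2 → 84.3% |
| 0.5 | 99.2 → 99.7% | 0.861 | 80.3 → 85.7% |

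The efficiency gain is 1/ratio − 1, from 1/0.983 − 1 = 2% to 1/0.861 − 1 = 16%. The 28% rate is an assumption; it is not in the SAP.

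A second simulation modelled the score itself: Baseline about N(3.7, 0.8), slope of Week 16 on Baseline 0.4 to 0.7, residual SD 0.8 to 1.0, with region and prior TNF inhibitor exposure in both models. It gave mean Wald Z of 3.82–3.87 without Baseline and 3.94–4.17 with it, a gain of 5 to 16%. At 28%, power rose from 81–82% to 84–87%. Repeat runs of these settings without the stratification terms gave about 3 to 20% in efficiency and about 0.5 to 6 power points at 28%. The 84–87% therefore belongs to the more favourable settings.

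**4. Standard error of the log odds ratio.** In the first simulation, at the SAP rates, it rises with adjustment from about 0.326 to 0.332 (r = 0.2) and 0.357 (r = 0.5). The conditional log odds ratio moves further from zero by more than this, which is why Z increases.

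**5. Chance imbalance.** In Baseline SD units, the between-arm difference has SD √(1/100 + 1/200) = 0.122, so a 2-sigma imbalance is 0.245. Without the covariate, each 1 SD of imbalance shifts the rate difference by 0.057 (r = 0.2) to 0.146 (r = 0.5). The shift is 0.245 × 0.057 = 1.4 points to 0.245 × 0.146 = 3.6 points. With the covariate it is about zero.

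**6. Validity of the current model.** Simulated type I error without Baseline was 4.4 to 4.9%.

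**The case against.** The other side has a good case. Section 4.1 sets one policy, and sections 4.2.1.4.1, 8.1.2 and 8.2.2 follow it, so nothing is contradicted. At the planned rates the endpoint has 98% power, and the covariate adds at most about half a point in the table above. The larger gains need a 28% bimekizumab rate and a Baseline distribution that the SAP does not contain; at r = 0.2 there is almost no gain. Baseline ASDAS is tabulated by arm, used as a subgroup, and adjusted for in the nominal ASDAS-CRP analysis. ASAS40, ASAS20 and ASAS5/6 also measure improvement from Baseline and use the same model. Because response is impossible below 2.636, a linear Baseline term on the logit scale is only approximate.

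Most of this stands as a limit on size. It does not remove the point. The tables, the subgroup analysis and the nominal ANCOVA do not change the hierarchical test or its reported odds ratio. The ASAS responses combine several component scores, whereas ASDAS-MI is one score with one absolute cut, so the covariate is obvious and already derived. An approximate term can still recover part of the loss.

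A reader might infer that the planned comparison is biased or its error rate inflated. It is not: chance imbalance averages out over randomisations and the simulated type I error is at or just under 5%. A reader might also infer that the odds ratio would be estimated with a smaller standard error after adjustment; the opposite holds. Nor does the SAP rank predictors, so it cannot support calling Baseline ASDAS-CRP the strongest one.

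**Conclusion.** The omission is real, and the dependence on Baseline follows from the SAP's own formula. The cost is modest: about 2 to 20% in efficiency, under 1 power point at 36% vs 13.8%, and about 0 to 6 points if the bimekizumab rate were 28%. These ranges rest on assumed Baseline-outcome relations. The gain lies in the test statistic and in the precision of the adjusted rate difference. The imbalance correction, up to about 1.4 to 3.6 points for a 2-sigma difference, is useful at any power.

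It would go too far to say that the omission endangers the testing sequence. Under the SAP's own assumptions ASDAS-MI passes about 99% of the time with either model. This is a low-severity efficiency improvement, not an error.

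**What to change.** Before unblinding, state in section 8.2.2 that the ASDAS-MI logistic model includes continuous Baseline ASDAS-CRP in the NRI, MI and observed-case analyses. Where Baseline is missing, use the Screening value under section 3.3 and otherwise the overall Baseline mean, so that no randomised participant drops out of the NRI model. Keep the current model as a supportive run for continuity with the other binary endpoints.

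The cost is one model term and a sentence or two; no new data are needed. The downside is that the odds ratio becomes conditional on Baseline ASDAS-CRP as well, so it is no longer the same quantity as in the other binary models. That is why the covariate has to be fixed in advance.
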